## Device Responsibilities

Access to the investigational device will be restricted to the investigators, and the device must be used exclusively in accordance with this protocol.

The sponsor must keep track of the device's location, which may be returned to the manufacturer for inspections or updates following the assessments described in this clinical investigation plan. The device will then be returned to the sponsor/principal investigator for the continuation of the study once the necessary inspections or updates by the manufacturer have been completed.

In the event that device inspection by the manufacturer is deemed necessary at the request of the Principal Investigator or the advisory board, documents should be prepared, including:

1. Date of submission to the manufacturer.
2. Number of the last subject enrolled in the study.
3. Date of receipt from the manufacturer.

23

## Clinical Investigation Plan

Automatic Control of Total Intravenous Anesthesia: Closed-loop Delivery of Propofol and Remifentanil Using Bispectral Index as Feedback Variable.

Acronym: ACTIVA 2. Id code: NP-2861. NCT number: NCT04432974.

4. Report from the manufacturer regarding the device inspection and any modifications or updates to the ACTIVA software.

Once the device has been received, the trial may continue with communication to the relevant authorities.

## Declaration of Compliance

The clinical investigation involving the ACTIVA software will be conducted under conditions similar to the normal conditions of device use, and the procedures used for conducting the clinical investigation are appropriate for the device under examination.

During the planning of the clinical investigation, all relevant characteristics, including those related to device safety, performance, and potential effects on the patient, have been examined, and these characteristics will be monitored throughout the duration of the investigation.

The clinical investigation will be conducted according to an appropriate clinical protocol that takes into account the current state of scientific and technical knowledge and is designed to confirm or refute the manufacturer's claims regarding the device. This investigation includes a sufficient number of observations to ensure the scientific validity of the conclusions.

The clinical investigation, with regard to the responsibility of the manufacturer/authorized representative, will be conducted in accordance with the provisions of Annexes VIII and X of Legislative Decree February 24, 1997, no. 46 and subsequent amendments, and Annexes 6 and 7 of Legislative Decree December 14, 1992, no. 507 and subsequent amendments, in compliance with the Declaration of Helsinki, as well as applicable sections of the ICH/GCP guidelines, UNI EN ISO 14155-2012, and subsequent updates or other internationally recognized equivalent standards. This will occur only after approval by the competent Ethics Committee of the experimental protocol, informed consent text, and documentation required by the aforementioned standards.

The medical device complies with the essential requirements as defined by current regulations, except for aspects that are the subject of the investigation. Necessary precautions have been taken to protect the health and safety of the patient.

Risk assessment has been performed in accordance with UNI EN ISO 14971:2012 and subsequent amendments, and all necessary measures have been taken to minimize these risks.

All serious adverse events will be fully recorded and immediately reported to the 6th Office of the DGDMF of the Ministry of Health and to all other competent authorities of the member states involved in the clinical investigation, in accordance with point 2.3.5 of Annex 7 of Legislative Decree December 14, 1992, no. 507 and subsequent amendments, and point 2.3.5 of Annex X of Legislative Decree February 24, 1997, no. 46 and subsequent amendments.

All financial burdens related to the clinical investigation are borne by the manufacturer and do not fall on the National Health Service or the patients.

The Clinical Trial Office of the Ministry of Health and the competent ethics committees will receive the final report prepared by the investigator at the end of the clinical investigation, including a critical evaluation of all data obtained during the study. This clinical investigation plan is prepared in accordance with UNI EN ISO 14155:2012 and subsequent updates.

## Clinical Investigation Plan

Automatic Control of Total Intravenous Anesthesia: Closed-loop Delivery of Propofol and Remifentanil Using Bispectral Index as Feedback Variable.

Acronym: ACTIVA 2. Id code: NP-2861. NCT number: NCT04432974.

Documents for obtaining informed consent have been prepared and have undergone evaluation by the competent Ethics Committee.

The manufacturer undertakes to make available to the Ministry of Health the dossier for the investigator and complete documentation related to risk analysis.

The manufacturer commits to provide the Ministry with all relevant information regarding the ACTIVA software, including the design, manufacturing methods, and descriptions and explanations necessary for understanding the aforementioned designs and schematics and the product's operation; the results of design calculations, controls, technical tests performed, and similar assessments conducted.

## Vulnerable Population and Treatments in Emergency Circumstances

Not applicable.

## Early Termination and Suspension of the Clinical Investigation

The clinical investigation may terminate prematurely in the event that:

1. Patient enrollment occurs at a faster rate than anticipated.
2. The ACTIVA software is found to be unreliable or unfeasible in a clinical setting with no possibility of correction.
3. Risks emerge that necessitate the immediate termination of the clinical investigation with no possibility of mitigating or eliminating these risks.

The clinical investigation may be suspended in the event that:

1. The ACTIVA software exhibits reliability, safety, or feasibility issues that warrant reevaluation by the manufacturer but are considered solvable.
2. Whenever the investigator deems it necessary to suspend the study, deferring the decision on resumption to the Principal Investigator. The Principal Investigator will analyze the reasons and determine a possible solution, possibly after consultation with the manufacturer and the advisory board."

## Data Publication Policy

The results of the clinical investigation will be submitted for publication in scientific journals after the study is completed, and the data have been analyzed according to the statistical plan.

Publication may be sought in journals specializing in anesthesia and intensive care, anesthesia and analgesia, or national and international surgical journals.

Additionally, publication may be sought in other scientific journals deemed suitable by the manufacturer, even if the manufacturer has not previously published in those journals.

## Clinical Investigation Plan

Automatic Control of Total Intravenous Anesthesia: Closed-loop Delivery of Propofol and Remifentanil Using Bispectral Index as Feedback Variable.

Acronym: ACTIVA 2. Id code: NP-2861. NCT number: NCT04432974.

### Clinical Investigation Plan

Automatic Control of Total Intravenous Anesthesia: Closed-loop Delivery of Propofol and Remifentanil Using Bispectral Index as Feedback Variable.

Acronym: ACTIVA 2. Id code: NP-2861. NCT number: NCT04432974.

Statistical Analysis Plan

Study title	Automatic Control of Total Intravenous Anesthesia: Closed-loop Delivery of Propofol and Remifentanil Using Bispectral Index as Feedback Variable. Acronym: ACTIVA 2.
Identifier code of the clinical investigation	NP-2861
Version number of the clinical investigation	Version 4
Version date	07/03/2019
NCT number	NCT04432974
Sponsor	Azienda Socio Sanitaria Territoriale degli Spedali Civili di Brescia
Principal investigator	[name] Medical specialist in anesthesia and intensive care medicine at the 2nd Department of Anesthesia and Intensive Care, ASST Spedali Civili di Brescia.
Location	Azienda Socio Sanitaria Territoriale degli Spedali Civili di Brescia, 25123, Brescia, Italy.
Author of the document	[name]
Document date	17/06/2020

Statistical Analysis Plan

Automatic Control of Total Intravenous Anesthesia: Closed-loop Delivery of Propofol and Remifentanil Using Bispectral Index as Feedback Variable.
Acronym: ACTIVA 2. Id code: NP-2861. NCT number: NCT04432974.

Index

List of abbreviations.....	3
Introduction.....	3
Study design.....	4
Sample size calculation.....	5
Aims and objectives.....	5
Outcomes.....	5
Population to be analyzed.....	6
Analyses.....	7
Data management.....	8

Statistical Analysis Plan

Automatic Control of Total Intravenous Anesthesia: Closed-loop Delivery of Propofol and Remifentanil Using Bispectral Index as Feedback Variable.

Acronym: ACTIVA 2. Id code: NP-2861. NCT number: NCT04432974.

List of abbreviations

ACTIVA = automatic control of total intravenous anesthesia;

BIS = bispectral index scale;

GUI = graphical user interface;

HR = heart rate;

MBP = mean blood pressure;

PONV = postoperative nausea and vomiting.

Introduction

This study concerns the clinical evaluation of a closed loop control system for the automatic administration of anesthetic drugs in TIVA (Total Intravenous Anesthesia). The purpose of the experimentation is to demonstrate that the control system under study is reliable, safe, applicable and capable of inducing and maintaining an optimal anesthetic level.

Statistical Analysis Plan

Automatic Control of Total Intravenous Anesthesia: Closed-loop Delivery of Propofol and Remifentanil Using Bispectral Index as Feedback Variable.

Acronym: ACTIVA 2. Id code: NP-2861. NCT number: NCT04432974.

Study design

The clinical study ACTIVA 2 is a pragmatic, interventional, nonrandomized, single-arm, single-center.

The population considered in the clinical study consists of adult patients scheduled for elective surgery for whom total intravenous general anesthesia is indicated, using the hypnotic drug propofol and the analgesic drug remifentanil, and who have provided appropriate informed consent. Patients under the age of 18 and patients incapable of understanding and consenting are excluded from the study.

The selection of patients is made regardless of age (provided they are over 18), gender, weight, height, as well as anesthetic risk and the type of surgical procedure. This reduces systematic errors associated with specific patient selection for enrollment in the study.

The enrolled patients underwent an anesthesiological treatment conducted in a closed-loop system following the clinical protocol and under the constant supervision of the experimenter. The experimentation took place in a single operating room at the experimenter's center where plastic surgery procedures are performed. This allowed for maintaining a consistent surgical and environmental setting.

Patients are informed of the possibility to participate in the study during the preoperative anesthesia visit, which typically occurs two weeks before the surgical procedure. If the patient chooses to participate in the study, informed consent is obtained before the start of the medical procedure subject to the experimentation.

The patient enrolled in the study arrives in the operating room on the day of the procedure and undergoes the standard preoperative preparation, which is administered to all patients undergoing intravenous general anesthesia, regardless of their enrollment in the study. In particular:

- Venous access is established.
- Instrumental monitoring includes blood pressure, electrocardiogram, peripheral oxygen saturation, and Bispectral Index Scale (BIS).
- Infusion pumps are connected to the venous access.

The ACTIVA control software is then initiated by the lead experimenter, who enters the necessary anthropometric data into the GUI, initializes the system, and starts the automatic control. During the surgical phase, the experimenter supervises the system and ensures its proper functioning. If necessary, annotations are added to the system according to the protocol. Once the surgical procedure is completed, the experimenter stops the drug infusions through the graphical user interface (GUI) but continues recording the BIS and other patient monitoring parameters. The patient awakens spontaneously. After awakening, the ACTIVA software is turned off by the experimenter.

The patient is then transferred to the recovery room where they undergo standard post-operative procedures. The study concludes 24 hours after the patient awakens from anesthesia with a postoperative anesthesia visit.

Statistical Analysis Plan

Automatic Control of Total Intravenous Anesthesia: Closed-loop Delivery of Propofol and Remifentanil Using Bispectral Index as Feedback Variable.

Acronym: ACTIVA 2. Id code: NP-2861. NCT number: NCT04432974.

Sample size calculation

The sample size was determined based on the primary outcome measure concerning the depth of hypnosis adequacy provided by the ACTIVA control software. Specifically, it was calculated with the aim to assess the proportion of patients for whom the percentage of the anesthesia maintenance duration in which the BIS is kept inside the recommended range from 40 to 60 is greater than 43%. This latter value is the average percentage that was observed in a previous data acquisition campaign concerning manually controlled TIVA, which was performed in the same clinical setting considered for the present clinical trial (Study acronym: ACTIVA 1, Id code: NP-1843).

The proportion was estimated to be 90% of patients with a 95% confidence interval and a margin of error of 10%. The resulting sample size is 139 patients. This number of enrolled subjects also ensures that the ACTIVA control software is adequately tested for safety, reliability, feasibility, and applicability. Secondary outcome measures were not considered in the sample size calculation.

Aims and objectives

The primary objective of the clinical investigation is to investigate the clinical performances obtainable by the control system under study in terms of depth of hypnosis adequacy.

The secondary objective is to evaluate the reliability, safety and applicability of the control system under study and to carry out the clinical evaluation of the automatic control system during the induction, maintenance and recovery of general intravenous anesthesia.

Outcomes

The primary outcome measure is the depth of hypnosis adequacy. It is assessed by means of the percentage of the anesthesia maintenance duration in which the BIS is kept inside the recommended range from 40 to 60. The percentage of the anesthesia maintenance duration in which the BIS is kept below 40 is also specified. Maintenance duration is the period of time that goes from the end of anesthesia induction to the point at which the automatic control is turned off at the conclusion of surgery. The end of anesthesia induction is defined as the time instant when the BIS drops below 40 for the first time and remains there for the subsequent 30 seconds.

The secondary outcomes measures are:

- Number and types of dysfunctions of the ACTIVA automatic infusion system.
- Level of satisfaction of the experimenter. It is expressed on a scale from 0 to 10 regarding the ease of use of the ACTIVA software and its infusion system, the induction phase of anesthesia and the maintenance phase of anesthesia.
- Effect of drugs delivery on heart rate. It is assessed by means of the percentage of the anesthesia maintenance duration in which the heart rate (HR) is kept inside the range from 50 to 100 beats per minute. The percentage of the anesthesia maintenance duration in which the HR is kept below 50 is also specified.

Statistical Analysis Plan

Automatic Control of Total Intravenous Anesthesia: Closed-loop Delivery of Propofol and Remifentanil Using Bispectral Index as Feedback Variable.

Acronym: ACTIVA 2. Id code: NP-2861. NCT number: NCT04432974.

- Effect of drugs delivery on mean blood pressure. It is assessed by means of the percentage of the anesthesia maintenance duration in which the non-invasively measured mean blood pressure (MBP) is kept inside the range from 65 to 110 mmHg. The percentage of the anesthesia maintenance duration in which the MBP is kept below 65 is also specified.
- Postoperative heart rate stability. It is assessed by measuring the HR in bpm.
- Postoperative Mean Blood Pressure Stability. It is assessed by non-invasive measuring of the mean blood pressure in mmHg.
- Postoperative sedation. It is assessed by means of a Sedation Score scale. It is a 3 point scale from 0 (fully awake) to 3 (fully sedated).
- Postoperative nausea and vomiting (PONV). It is assessed by means of the Bellville PONV scale. It is a 3 point scale from 0 (no nausea and vomiting) to 3 (vomiting present).
- Postoperative analgesia. It is assessed using a 10-point numeric rating scale (NRS). It is a 10 point scale from 0 (no pain) to 10 (maximum pain).

Population to be analyzed

The population considered in the clinical study consists of adult patients scheduled for elective surgery for whom total intravenous general anesthesia is indicated, using the hypnotic drug propofol and the analgesic drug remifentanil, and who have provided appropriate informed consent. Patients under the age of 18 and patients incapable of understanding and consenting are excluded from the study.

The selection of patients is made regardless of age (provided they are over 18), gender, weight, height, as well as anesthetic risk and the type of surgical procedure. This reduces systematic errors associated with specific patient selection for enrollment in the study.

The enrolled patients underwent an anesthesiological treatment conducted in a closed-loop system following the clinical protocol and under the constant supervision of the experimenter. The experimentation took place in a single operating room at the experimenter's center where plastic surgery procedures are performed. This allowed for maintaining a consistent surgical and environmental setting.

Patients are informed of the possibility to participate in the study during the preoperative anesthesia visit, which typically occurs two weeks before the surgical procedure. If the patient chooses to participate in the study, informed consent is obtained before the start of the medical procedure subject to the experimentation.

The patient enrolled in the study arrives in the operating room on the day of the procedure and undergoes the standard preoperative preparation, which is administered to all patients undergoing intravenous general anesthesia, regardless of their enrollment in the study. In particular:

- Venous access is established.
- Instrumental monitoring includes blood pressure, electrocardiogram, peripheral oxygen saturation, and BIS (Bispectral Index).

Statistical Analysis Plan

Automatic Control of Total Intravenous Anesthesia: Closed-loop Delivery of Propofol and Remifentanil Using Bispectral Index as Feedback Variable.

Acronym: ACTIVA 2. Id code: NP-2861. NCT number: NCT04432974.

- Infusion pumps are connected to the venous access.

The ACTIVA control software is then initiated by the lead experimenter, who enters the necessary anthropometric data into the GUI, initializes the system, and starts the automatic control. During the surgical phase, the experimenter supervises the system and ensures its proper functioning. If necessary, annotations are added to the system according to the protocol. Once the surgical procedure is completed, the experimenter stops the drug infusions through the GUI but continues recording the BIS and other patient monitoring parameters. The patient awakens spontaneously. After awakening, the ACTIVA software is turned off by the experimenter.

The patient is then transferred to the recovery room where they undergo standard post-operative procedures. The study concludes 24 hours after the patient awakens from anesthesia with a postoperative anesthesia visit.

Analyses

For each patient enrolled in the study, the following variables will be collected:

- Age.
- Gender.
- Weight
- Height
- Type of surgical procedure
- Anesthesiological risk assessment according to the American Society of Anesthesiologists physical status classification system.
- PONV risk assessment according to the Apfel simplified risk score.

These data are collected by the principal investigator at patient arrival in the operating room, before surgery and they are noted on the patient's anesthesiology clinical record form.

The following variables are automatically collected by the ACTIVA software, they are recorded in real-time every second and stored on a ".csv" file:

- HR.
- Peripheral oxygen saturation.
- MBP.
- BIS.
- BIS signal quality index.
- Burst suppression ratio¹.
- Infusion rates of propofol and remifentanil.

¹ Burst suppression is defined as a period on the electroencephalogram trace characterized by attenuated or suppressed signal (<10 mV) alternating with brief periods of cortical activity, precisely termed 'bursts.' More than 50% of this period is dominated by attenuated/suppressed activity. This effect may sometimes be intentionally induced, for example, during neuroanesthesia, as a protective measure against cerebral ischemia, as it coincides with a reduction in cerebral metabolism. However, it is important to consider that it is also associated with a higher incidence of postoperative delirium.

Statistical Analysis Plan

Automatic Control of Total Intravenous Anesthesia: Closed-loop Delivery of Propofol and Remifentanil Using Bispectral Index as Feedback Variable.

Acronym: ACTIVA 2. Id code: NP-2861. NCT number: NCT04432974.

The following data are collected by the principal investigator after surgery and noted on the patient's anesthesiology clinical record form.

- System dysfunctions.
- Level of satisfaction of the experimenter.
- HR.
- MBP.
- Postoperative sedation.
- PONV.
- Postoperative analgesia.

Descriptive statistics will be performed on all study variables.

Quantitative data will be presented as mean (SD) or median (IQR) according to their distribution. Normality of the data will be tested using a Shapiro-Wilk test. Categorical data will be presented as frequency (proportion).

Data management

The data management activities have been carried out in such a way as to ensure that data processing is complete, consistent, and logical, and that all data described in the clinical investigation are included in the study. The file recorded by the ACTIVA control software allows for the analysis of the control system's performance regarding malfunctions and/or critical issues identified by the experimenter, recorded in the form of notes. Furthermore, it contains recordings of time series data for drug infusion rates, BIS (Bispectral Index), and other standard monitoring data for general anesthesia. The report file allows for offline analysis of the control system's performance. The report file is generated automatically by the ACTIVA control software. Post-operative data, on the other hand, are manually recorded by the experimenter on the designated data collection sheet. Experimenters have filled out the data collection sheet and entered notes on the GUI during the operation of the ACTIVA software as prescribed. During the conduct of the clinical study, the data resulting from the study are stored by the lead experimenter in their original form on the PC dedicated to the ACTIVA software and backed up on the experimenter center's PC. At the end of the study, all data have been migrated and are stored on a dedicated PC at the experimenter center. Access to the data is restricted to authorized individuals.

Statistical Analysis Plan

Automatic Control of Total Intravenous Anesthesia: Closed-loop Delivery of Propofol and Remifentanil Using Bispectral Index as Feedback Variable.

Acronym: ACTIVA 2. Id code: NP-2861. NCT number: NCT04432974.

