### Clinical study description

The clinical study ACTIVA 2 is a pragmatic, interventional, nonrandomized, single-arm, single-center.

The investigation is for research purposes (for publication in scientific journals), non-commercial, and for clinical development of the ACTIVA control software.

The primary outcome measure is the depth of hypnosis adequacy. It is assessed by means of the percentage of the anesthesia maintenance duration in which the BIS is kept inside the recommended range from 40 to 60. The percentage of the anesthesia maintenance duration in which the BIS is kept below 40 is also specified. Maintenance duration is the period of time that goes from the end of anesthesia induction to the point at which the automatic control is turned off at the conclusion of surgery. The end of anesthesia induction is defined as the time instant when the BIS drops below 40 for the first time and remains there for the subsequent 30 seconds.

The secondary outcomes measures are:

- Number and types of dysfunctions of the ACTIVA automatic infusion system.
- Level of satisfaction of the experimenter. It is expressed on a scale from 0 to 10 regarding the ease of use of the ACTIVA software and its infusion system, the induction phase of anesthesia and the maintenance phase of anesthesia.
- Effect of drugs delivery on heart rate. It is assessed by means of the percentage of the anesthesia maintenance duration in which the heart rate (HR) is kept inside the range from 50 to 100 beats per minute. The percentage of the anesthesia maintenance duration in which the HR is kept below 50 is also specified.
- Effect of drugs delivery on mean blood pressure. It is assessed by means of the percentage of the anesthesia maintenance duration in which the non-invasively measured mean blood pressure (MBP) is kept inside the range from 65 to 110 mmHg. The percentage of the anesthesia maintenance duration in which the MBP is kept below 65 is also specified.
- Postoperative heart rate stability. It is assessed by measuring the HR in bpm.
- Postoperative Mean Blood Pressure Stability. It is assessed by non-invasive measuring of the mean blood pressure in mmHg.

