### Clinical Investigation Plan

Automatic Control of Total Intravenous Anesthesia: Closed-loop Delivery of Propofol and Remifentanil Using Bispectral Index as Feedback Variable.

Acronym: ACTIVA 2. Id code: NP-2861. NCT number: NCT04432974.

- Postoperative sedation. It is assessed by means of a Sedation Score scale. It is a 3 point scale from 0 (fully awake) to 3 (fully sedated).
- Postoperative nausea and vomiting (PONV). It is assessed by means of the Bellville PONV scale. It is a 3 point scale from 0 (no nausea and vomiting) to 3 (vomiting present).
- Postoperative analgesia. It is assessed using a 10-point numeric rating scale (NRS). It is a 10 point scale from 0 (no pain) to 10 (maximum pain).

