## Measured variables

For each patient enrolled in the study, the following variables will be collected:

- Age.
- Gender.
- Weight
- Height
- Type of surgical procedure
- Anesthesiological risk assessment according to the American Society of Anesthesiologists (ASA) physical status classification system.
- PONV risk assessment according to the Apfel simplified risk score.

These data are collected by the principal investigator at patient arrival in the operating room, before surgery and they are noted on the patient's anesthesiology clinical record form.

The following variables are automatically collected by the ACTIVA software, they are recorded in real-time every second and stored on a ".csv" file:

- HR.
- Peripheral oxygen saturation.
- MBP.
- BIS.
- BIS signal quality index (SQI).
- Burst suppression ratio.
- Infusion rates of propofol and remifentanil.

The following data are collected by the principal investigator after surgery and noted on the patient's anesthesiology clinical record form.

- System dysfunctions.
- Level of satisfaction of the experimenter.
- HR.
- MBP.
- Postoperative sedation.

---

 Burst suppression is defined as a period on the EEG trace characterized by attenuated or suppressed signal (<10 mV) alternating with brief periods of cortical activity, precisely termed 'bursts.' More than 50% of this period is dominated by attenuated/suppressed activity. This effect may sometimes be intentionally induced, for example, during neuroanesthesia, as a protective measure against cerebral ischemia, as it coincides with a reduction in cerebral metabolism. However, it is important to consider that it is also associated with a higher incidence of postoperative delirium.

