## Statistical analysis

The statistical analysis consists in the descriptive statistics of the collected data.

Synthetic statistical data are calculated for all study variables.

For quantitative data mean and standard deviation, or median and interquartile range are calculated according to data distribution. Data normality is checked by using the Shapiro-Wilk test.

Categorical variables are synthesized by using patient count and percentage of patients belonging to each category.

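### If fewer than about a quarter of patients have any time with MBP below 65 or HR below 50, the planned summary reads median 0 (IQR 0-0) and does not show how many were affected or for how long

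*SAP*

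**What the plan says.** The SAP, under Analyses, states "Descriptive statistics will be performed on all study variables". It then sets the format: "Quantitative data will be presented as mean (SD) or median (IQR) according to their distribution". The choice between the two rests on a test: "Normality of the data will be tested using a Shapiro-Wilk test". No significance level is given for that test. The protocol, under Statistical analysis, carries the same rule: "For quantitative data mean and standard deviation, or median and interquartile range are calculated according to data distribution". Both documents reserve counts and percentages for categorical variables.

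The two measures at issue are secondary outcomes, defined in the protocol under Clinical study description and in the SAP under Outcomes. For blood pressure: "The percentage of the anesthesia maintenance duration in which the MBP is kept below 65 is also specified". For heart rate: "The percentage of the anesthesia maintenance duration in which the HR is kept below 50 is also specified". Each gives one percentage per patient with a floor at zero, so each falls under the quantitative rule. Neither document plans a count of patients with any time below the limit, an upper percentile or a maximum for these measures.

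**The concern.** Time below a safety limit is often a measure on which many patients score exactly zero and the clinically important exposure sits in a minority. If that happens here, normality is rejected and the rule selects median (IQR). Those three quartiles describe the patient in the middle and the patients a quarter of the way in from each end. They carry no information on the highest quarter, which is where a hemodynamic problem with the controller would show.

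Safety is part of the stated secondary objective. The protocol describes this as the first clinical investigation of the system and names less hypotension as a possible benefit. The study has one arm and a purely descriptive analysis, so these summaries are its planned tabulated evidence on intraoperative low blood pressure and slow heart rate. A row of zeros could be taken as support for the hoped-for benefit when the data do not warrant it.

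**Working it through.** **Inputs.** N = 139 (protocol, Number of patients enrolled; SAP, Sample size calculation). The summary rule and outcome definitions are as quoted. The documents give no distribution for either measure, so every patient-level value below is assumed. Shapiro-Wilk is judged at 0.05, also assumed.

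**The plan's own figure.** n = z²p(1−p)/d² with z = 1.96 and p = 0.90. With d = 0.05, n = 138.29, rounded up to 139. With d = 0.10, n = 34.57, rounded up to 35. The planned 139 therefore reproduces as an interval of plus or minus 5 points. It is taken as given here.

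**When the quartiles are all zero.** Under the common interpolation rule the 75th percentile lies at position 1 + 0.75 × 138 = 104.5 in the ordered values, halfway between the 104th and 105th. It is zero if at least 105 patients score zero, that is, if at most 139 − 105 = 34 are affected (34/139 = 24.5%). Eight of nine standard quantile definitions give 34; the ninth gives 35 (25.2%). The median is the 70th value, so it stays zero with up to 139 − 70 = 69 affected (49.6%).

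**Whether such data go to median (IQR).** In simulations of 139 patients (2,000 per setting, non-zero values from an assumed skewed distribution), Shapiro-Wilk rejected in every sample with at least one non-zero value. The largest p was 3.3e-16 with an expected 75% zeros and 8.4e-12 with 50%. Even when 35 non-zero values were placed to look as normal as possible, p was 6.5e-18. The unstated test level therefore makes no practical difference.

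**What the table would show.** Affected patients are spread evenly from 5% to 60% of maintenance; the rest are zero.

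| Affected | Planned summary | Mean (SD) | Affected, % (exact 95% CI) |
|---|---|---|---|
| 14 | 0 (0-0) | 3.3 (11.2) | 10.1 (5.6 to 16.3) |
| 28 | 0 (0-0) | 6.5 (15.0) | 20.1 (13.8 to 27.8) |
| 34 | 0 (0-0) | 7.9 (16.2) | 24.5 (17.6 to 32.5) |
| 35 | 0 (0-2.5) | 8.2 (16.4) | 25.2 (18.2 to 33.2) |
| 42 | 0 (0-13.7) | 9.8 (17.5) | 30.2 (22.7 to 38.6) |

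The first three rows are identical in the planned format, although the number affected rises from 14 to 34.

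**Above a quarter affected.** Take two data sets, each with 83 zeros, 22 values from 0.5% to 5%, and 34 further patients. In one the 34 run from 5% to 8%; in the other, from 5% to 60%. Both report median 0 (IQR 0-4.9). Their 90th percentiles are 6.7% and 37%, and their maxima 8% and 60%. The planned summary cannot tell these apart.

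**The case against.** The strongest reply is that the zero-heavy shape is assumed. That stands. The documents give no rates, they treat hypotension as a recognised effect of general anesthesia, enrolment is open to any anesthetic risk, and values are stored every second, so one brief dip makes a patient non-zero. MBP below 65 may well affect more than a quarter of patients, and the IQR would then not read 0-0. What survives is the second half of the point: the severity of the worst quarter stays invisible at any share affected.

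It is also fair to say that the normality test is not the root cause. Mean (SD) would not give the number affected either. The gap is that nothing is planned beside the chosen summary, although the plan does not forbid adding to it.

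A reader might infer that the trial would report no hypotension and no bradycardia. The documents do not support that. A median of 0 (0-0) makes no such statement, and there are other safety channels: adverse event reporting, an advisory board and monthly review of safety notes. None of these is described as tabulating time below the limits.

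Three extensions are tempting and also fail.

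- "Burst suppression ratio" is only a recorded variable. It is not a listed outcome and has no per-patient summary, so how it would read under the rule cannot be determined.
- The nausea and vomiting score ("It is a 3 point scale from 0 (no nausea and vomiting) to 3 (vomiting present") and the sedation score fit the existing rule of counts per category, and nothing says they will be treated as quantitative.
- The in-range percentages would read 100 (100-100) only if fewer than about a quarter of patients left the range in either direction. That is a stricter condition, because time above the upper limit counts too.

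**Conclusion.** The concern holds for two measures, in conditional form. At 139 patients, if at most 34 (24.5%) have any maintenance time with MBP below 65, the planned result is median 0 (IQR 0-0), and it shows neither how many patients were affected nor for how long. The same holds separately for HR below 50. Above that share the IQR opens up but remains silent on the worst quarter. The quartile limit is arithmetic and depends only on N and, by one patient, on the quantile definition. Whether the trial's data will fall below it is unknown. This is a worthwhile reporting correction on a stated safety objective. It does not affect the primary outcome or the sample size, and it is not evidence that the safety findings would be suppressed.

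**What to change.** Add to SAP Analyses, and in matching words to Protocol Statistical analysis: whatever the Shapiro-Wilk result, the per-patient percentages of maintenance time with MBP below 65 and with HR below 50 will also be reported as

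1. the number and percentage of patients with any time below the limit, with an exact 95% confidence interval; and
2. the 90th percentile and the maximum of the per-patient percentage.

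Both parts are needed. The count alone treats a momentary dip like a long episode. The 90th percentile alone can also be zero: at N = 139 it lies at position 1 + 0.9 × 138 = 125.2, so it is zero with up to 13 patients affected (139 − 126 = 13). An interval for a proportion is not foreign to this plan, since the sample size is built on one.

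The cost is one sentence in each document and a few table rows, from data the software already stores. The safety results may look less favourable than a row of zeros. Sample size, primary outcome and clinical conduct do not change.
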